### SECTION 3: ANALYSIS PLAN

**3.1.1 Power analysis.** Sample size requirements were calculated taking into account a unique design effect for the SWD, such that  $N_{sw} = Nu \times DE_{sw}$  (where  $Nu$  is the total number of students needed to detect the treatment effect with a power of 80% and a significance level of 0.05, uncorrected for cluster and repeated measurements). The design effect was calculated as:

$$DE_{sw} = \frac{1 + \rho(ktn + bn - 1)}{1 + \rho\left(\frac{1}{2}ktn + bn - 1\right)} \times \frac{3(1 - \rho)}{2t(k - \frac{1}{k})}$$

where  $k$  is the number of steps,  $n$  is the expected number of students per cluster,  $b$  is the number of baseline measurements,  $t$  is the number of measurements after each step, and  $\rho$  is the intra-class correlation coefficient, estimated to be 0.016 based on findings reported by Kaufman et al. With an  $\rho$  of 0.05, power of 0.8,  $Nu = 292$ ,  $DE_{sw} = 1.3273$ , and the expectation of 15% attrition during the study, a sample size of 456 will allow the detection of a 0.14 increase in the proportion of condom use relative to the frequency of sexual intercourse from baseline to the 12-month observation period hypothesized under Aim 2.

**3.1.2 Missing data.** Attrition is likely to covary with truancy, suggesting a missing data mechanism that is not missing at random (NMAR). To address this, a dropout variable  $D_i$  will be developed for each individual across the 4 observation periods, where  $D_i=k$  for dropout between the  $(k-1)$  and  $k^{\text{th}}$  occasion. A model of the probability of dropout, where

$\log \left\{ \frac{\Pr(D_i=k \mid D_i \geq k, Y_{i1}, \dots, Y_{ik})}{\Pr(D_i>k \mid D_i > k, Y_{i1}, \dots, Y_{ik})} \right\} = \theta_1 + \theta_2 Y_{ik-1} + \theta_3 Y_{ik}$  presumes that  $\theta_3 \neq 0$  for the NMAR mechanism. Missing data will be examined using multiple imputation, where missing values are replaced by a set of  $m$  plausible values using a propensity scoring sequence to generate a single estimate of the parameters of interest. Observations will first be grouped on the basis of propensity score similarity, then individuals with missing values will be randomly matched to those with observed values, and finally missing values will be randomly selected with replacement from the random sample of observed values. This sequence will be repeated sequentially starting at the 3-month follow-up observation through the 12-month follow-up observation, and the entire propensity scoring and time imputation sequence(s) will be repeated at minimum across 2:5 datasets ( $m$ ) to estimate  $\bar{\beta} = \frac{1}{m} \sum_{k=1}^m \hat{\beta}^{(k)}$ . Sensitivity analyses will also be used to assess the robustness of primary results attributable to missing data by examining imputed and nonimputed data.

**3.1.3 Dose.** The treatment dose is the number of intervention components delivered to the individual student, accounting for individual students' attendance and participation. This will be tracked using the fidelity log, staff field notes, and the CAB meeting. A count, nominal, or weighted percentage will be used to represent dose pending analysis of the dose frequency distribution.

**3.1.4 Baseline data analysis.** Baseline data will first be analyzed to determine whether demographic and SRH variables vary relative to school (cluster). The psychometric properties of scales will be explored, and confirmatory factor analyses (CFA) for scales will be conducted. Finally, structural equation models (SEM) will

Woertman W et al. Stepped wedge designs could reduce the required sample size in cluster randomized trials. *J Clin Epidemiol*. July 2013;66(7):752-758.

Kaufman C et al. Effectiveness of Circle of Life, an HIV-preventive intervention for American Indian middle school youths. *Am J Public Health*. June 2014; 104(6):e106-e112.

be developed based on the multi-level components derived from the Ecological Systems Theory model

upon with the N/E was built. CFAs and SEMs will be conducted using Mplus software.

**3.1.5 Randomization of schools.** The 5 schools that AI youth from Fort Peck attend are the clusters to be randomized into the intervention, with all schools eventually being randomized to the intervention. Students and their parents/legal guardians will be recruited for baseline participation prior to randomization of the sites. Schools will be randomized to the intervention following baseline data collection using a single sequence random assignment to clusters that will determine order of intervention receipt.

**3.1.5 Generalized linear mixed-effects models.** To test for effectiveness of the *NIE* intervention across all hypotheses under Aim 2, the generalized linear mixed-effects models (GLMM) will be used to model binary primary and secondary outcomes (condom use under H1, condom use and other sexual risks under H2) and continuous tertiary outcomes (H3) in the data. The GLMM allows for individual-level binary and continuous responses to be modeled, key covariates to be controlled for, the specification of autocorrelation within individuals, and clustering by school. The GLMM is also the most frequently employed analytic method to adjust for the longitudinal nature of SWDs, and it was chosen over the Generalized Estimating Equations (GEEs) because GEEs show inflated Type 1 error rates when the number of clusters is small, as is the case with the number of schools at Fort Peck. Hussey and Hughes proposed a mixed-effects regression approach for the SWD-CRT design, where:

$Y_{ijl} = \mu + \beta_j + \theta X_{ij} + u_i + e_{ijl}$ , and where  $u_i \sim N(0, \sigma_u^2)$ ;  $e_{ijl} \sim N(0, \sigma_e^2)$ , with  $\beta_j$ =the fixed effect of time,  $X_{ij}$ =intervention (0,1 or dose representation),  $\theta$  =intervention effect,  $u_i$ =random effect for cluster, and  $e_{ijl}$ =residual for  $i$  clusters,  $j$  time periods, and  $l$  adolescents.  $Y_{ijl}$  will be modeled for SRH outcomes and interpreted in terms of a contrast of the log odds of response relative to AI youths with similar values for unobserved random effects. In order to test for changes in the tertiary outcomes, we will specify  $Y_{ijl}$  as continuous response outcomes. STATA statistical software will be used to conduct GLMMs. However, SAS will be used if more complex specification of the intraclass correlation becomes necessary.

**3.1.6 Analysis of focus group data.** Focus group data will be transcribed and coded using a partially inductive procedure. First, all transcript data will be open coded (line-by-line coding). The open codes will be pre-sorted based on whether participants are responding to acceptability or fidelity prompts. Within each implementation domain, axial codes will be developed to group the open codes, and the team will meet to discuss how axial codes saturate the pre-defined acceptability and fidelity categories. Transcripts will be coded using Atlas.ti software.

**3.2 Qualitative Data Analysis.** The systems level component and the FAS evaluation component of N/E will be analyzed using content analysis. Common themes will be identified from the two respective sets of data collection instruments. Coding will proceed in stages. A topical indexing scheme will be developed with input from the community advisory board members to identify the text pertaining to particular topics relevant to the systems level and FAS components of N/E. The software program, Atlis.ti will be used to construct and organize a topical indexing system of codes identifying sections of text that capture the central concepts of interests. Then, content coding will be developed by the research team with advice from the community



advisory board to capture the content, themes, or sentiment of responses within topics. The community advisory board members will receive copies of the content coding and the content, themes, and sentiment of responses for each of the themes identified in the qualitative data collection forms. Members of the research team, including the community advisory board, will individually identify themes from all text pertaining to a specific topic are related to N/E's AIMS 2 and 3 in order to then assist the research team in developing codes to be analyzed using Atlis.ti. The codes will be reviewed and approved of by the community advisory board prior to analysis. The coding reliability for the content coding will be determined through check coding of at least 20% of the randomly chosen text within major topical categories. Once the data are coded, the themes and patterns will be summarized and interpreted. Coded text will be used to identify illustrative quotes from the qualitative data collection materials.

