**Table 2. NIE Measures.**

**Table 2. N/E Measures.**

Data Collection Instruments and Measures	Data Collection: Baseline & Months				Description of Measures Number of Items; Scale Anchors; Benchmark Values	
	Base	3	9	12		
Student Survey						
Primary Outcome Variable						
Proportion of condom use during sexual intercourse (SI)	X	X	X	X	2 items; number of times condom used relative to number of times had SI	
Secondary Outcome Variables						
Age of onset of sexual intercourse	X	X	X	X	2 items; ever had SI & age at first SI	
Number of sex partners	X	X	X	X	2 items; lifetime & past-month sex partners	
Frequency of sexual intercourse	X	X	X	X	1 item; frequency of SI in past month	
Pregnancy history	X	X	X	X	1 item; number of pregnancies	
Type & frequency of birth control (BC) during sexual intercourse	X	X	X	X	3 items; type of BC use and number of times BC used during SI	
Type & frequency of substance use (SU) during sexual intercourse	X	X	X	X	1 item measures SU with SI; 5 items measure lifetime and past month SU	
Tertiary Outcome Variables						
Type & frequency of parent/legal guardian-child SRH communication	X	X	X	X	24 items Likert scale; higher score = higher communication	
Cultural identity & participation in cultural activities	X	X	X	X	3 items cultural identity ( $\alpha = .75$ ); 2 items cultural activities engagement ( $\alpha = .46$ )	
Type & frequency of SRH services	X	X	X	X	9 items; frequency, type, and follow-up of SRH services used	
Other Variables						
Motivation to avoid STIs, HIV, HCV, & pregnancy	X	X	X	X	Up to 9 items; 1 (very true) to 5 (very untrue); 1 = more positive attitude/motivation	
Condom & birth control use intention & self-efficacy	X	X	X	X	4 items per intention; 1 (very true) to 5 (very untrue); 1 = higher intention; 6 self-efficacy items; 1 (very easy) to 4 (very hard); 1 = high self-efficacy	
Abstinence	X	X	X	X	3 items; 1 (strongly disagree) to 4 (strongly agree); 4 = more supportive of teen abstinence	
Refusal skills regarding sex	X	X	X	X	7 items; 1 (I definitely can say no) to 5 (I definitely can't); 1 = stronger refusal skills	
Knowledge of STIs, HIV, HCV, pregnancy, & health relationships	X	X	X	X	Range of 4 to 10 items per topic; True/False/DK; Average proportion of questions correct	
Depression (CES-D) & exposure to stressful life events	X	X	X	X	CES-D — 7 items ( $\alpha = .80$ ); Life Events — 24 items; Yes/No; number of events observed	
Student Demographics						

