5.1 Have you ever had sexual intercourse? Yes No

*If you have never had sexual intercourse, skip to Section 6.*

5.2 How old were you when you had sexual intercourse for the first time?

- a. I have never had sexual intercourse
- b. 11 years old or younger
- c. 12 years old
- d. 13 years old
- e. 14 years old
- f. 15 years old
- g. 16 years old
- h. 17 years old or older

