5.3 During your life, with how many people have you had sexual intercourse?

- a. 1 person
- b. 2 people
- c. 3 people
- d. 4 people
- e. 5 people
- f. 6 or more people

5.4 During the past month, how many people have you had sex with? \_\_\_\_\_ [# of people]

5.5 During the past month, how many TIMES have you had sex? \_\_\_\_\_ times

5.6 Of the times you had sex over the past month, how many TIMES was a condom used?  
\_\_\_\_\_ times

5.7 Of the times you had sex over the past month, how many TIMES did you use birth control other than a condom, like birth control pills or having a deprova shot?  
\_\_\_\_\_ times

Over the past month, did you drink alcohol or take any kind of drug and have sex? Yes No

5.9 Did you drink alcohol or use drugs before you had sexual intercourse the **last** time?

- a. I have never had sexual intercourse
- b. Yes
- c. No

5.10 The last time you had sexual intercourse, what one method did you or the person you had sex with use to prevent pregnancy? (Select only one response.)

- a. No method was used to prevent pregnancy
- b. Birth control pills
- c. Condoms
- d. An IUD (such as Mirena or ParaGard) or implant (such as Implanon or Nexplanon)
- e. A shot (such as Depo-Provera), patch (such as OrthoEvra), or birth control ring (such as NuvaRing)
- f. Withdrawal or some other method
- g. Not sure

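### The primary condom-use ratio is undefined for students with no past-month intercourse, its conversion to a binary model outcome is unstated, and 456 makes no allowance for students without a ratio

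*Combined protocol and SAP*

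**What the plan says.** **Outcome.** Table 2 defines the primary outcome from two items: "number of times condom used relative to number of times had SI". In the student survey, item 5.5 asks "During the past month, how many TIMES have you had sex" and item 5.6 asks "Of the times you had sex over the past month, how many TIMES was a condom used". Item 5.1 instructs: "If you have never had sexual intercourse, skip to Section 6". A never-active student therefore leaves both items blank, and an experienced student can answer 0 to item 5.5.

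**Who is enrolled.** The inclusion criteria (Section 5, and again in 5.3.1) concern age, tribal membership, residence and school. None requires sexual activity. Aim 2 in 2.3.2 makes delayed onset and frequency of intercourse secondary outcomes, so students without intercourse are intended participants.

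**Sample size.** Section 3.1.1 states that "a sample size of 456 will allow the detection of a 0.14 increase in the proportion of condom use", from baseline to 12 months. The inputs are 292 students, a design effect of 1.3273 and 15% attrition.

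**Model.** Section 3.1.5 says that generalized linear mixed models "will be used to model binary primary and secondary outcomes (condom use under H1, condom use and other sexual risks under H2". The printed model has one response per cluster, period and adolescent, a log-odds interpretation, and a "random effect for cluster" as its only random effect besides the residual.

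**Missing data.** Section 3.1.2 begins from attrition and truancy and defines a dropout variable. It then describes imputation in which "missing values will be randomly selected with replacement from the random sample of observed values". Imputed and nonimputed data are to be compared as a sensitivity analysis.

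**Time point.** In the registration receipt in the appendices, H1 makes 12 months primary and 3 and 9 months secondary, and the progress report repeats this. The receipt's outcome list puts 3, 9 and 12 months all under the primary measure.

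**The concern.** There are three gaps.

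1. A ratio with a zero or skipped denominator has no value, and the plan gives no rule for students in that position. They could be left out, counted in some way, or given an imputed value. These choices lead to different primary estimates.

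2. Table 2 and the 0.14 describe a proportion of acts, while 3.1.5 describes a binary response. No cut-off (such as any use or always use) and no events-out-of-trials form is given. Two analysts could both follow the plan and fit different primary models, and the choice could be made after the data are seen.

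3. The sample size deducts attrition only. Enrolled students without a ratio use up places that the calculation counts as information.

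Leaving zero-act students out, which is the natural reading, also has a consequence that the plan does not mention. The primary comparison becomes conditional on past-month activity, which is measured after randomisation and which the intervention aims to change.

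**Working it through.** **Reproducing 456.** Inputs from 3.1.1: 292, 1.3273, 15%.
- 292 × 1.3273 = 387.57
- 387.57 / 0.85 = 455.97, rounded up to 456

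The 388 retained students are exactly the number that 292 × 1.3273 requires. No factor is left for undefined ratios.

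**Evaluable students.** Let f be the share of retained students with at least one act in the past month. The documents do not give f; 70%, 50% and 30% are assumed. Evaluable = 387.57 × f = 271 / 194 / 116. This does not depend on the design effect. Using one f for every survey is a simplification, since a student inactive at one survey can contribute at another.

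**Power at the stated design effect.** Calibrated to 80% at 292 with two-sided 0.05 (sidedness is not stated), power = Φ(2.8016 × √f − 1.96) and detectable difference = 0.14 / √f.

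| f | Evaluable | Power for 0.14 | Detectable difference |
|---|---|---|---|
| 100% | 388 | 80% | 0.140 |
| 70% | 271 | 65% | 0.167 |
| 50% | 194 | 51% | 0.198 |
| 30% | 116 | 34% | 0.256 |

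**Does 1.3273 fit the design?** The printed formula with ρ = 0.016 gives 1.3273 at k = 2, t = 1, b = 1, n = 71. Its first factor is below 2, so at k = 3 the design effect cannot exceed 2 × 3 × 0.984 / (2 × 2.667) = 1.107. The plan describes three waves (2.3.5) and also schools entering one at a time (2.3.2).

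**Power with the design effect recomputed.** Assumed: ρ = 0.016, b = 1, and n = 77.5 × f (387.57 / 5 schools × f). Power = Φ(2.8016 × √(387.57 × f / DE / 292) − 1.96).

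| k, t | f = 70% | f = 50% | f = 30% | f at which power is 80% |
|---|---|---|---|---|
| 3, 1 | 86% | 75% | 55% | 58% |
| 5, 1 | 98% | 92% | 77% | 33% |
| 3, 3 | 99.8% | 98.6% | 91% | 21% |
| 5, 3 | >99% | >99% | 99% | 11% |

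The plan gives no number for k or t. The conflict between 12 months alone and all three surveys as primary bears on t, as does the statement in 2.3.5 that clusters are followed at 3, 9 and 12 months once they have begun.

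**Selection, by example (assumed figures).** Of 100 students, 50 are active: 20 always use condoms, 30 never do, and all have equal numbers of acts. Condom use among the active is 20/50 = 40%. Suppose 10 active students stop having sex and nobody else changes. If all 10 were non-users, the share becomes 20/40 = 50%. If all 10 were users, it becomes 10/40 = 25%. The primary measure moves although no remaining student changed condom use.

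**The case against.** The best defence is that the outcome's wording already settles the matter. Condom use during intercourse, relative to the number of acts, leaves out students with no acts, and counting them as successes or failures would be strained. That is the natural reading, and I adopt it. But no section states it, and the sample size does not follow it.

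On imputation, 3.1.2 is motivated by dropout and can be read as confined to it. A reader might infer that the plan orders condom use to be imputed for abstinent students; the text does not go that far. It refers to missing values without distinguishing not applicable from lost, so it permits that result without requiring it.

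A reader might also infer that the trial is underpowered. The documents do not support this. The 65%, 51% and 34% need both a value of f that the documents lack and a design effect that does not correspond to three or five steps. With the formula recomputed, power may be above or below 80%.

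Nor does the missing binary definition by itself decide how zero-act students count. The cut-off and the zero-act rule are separate decisions. In the example above, leaving inactive students out gives 40% whether the outcome is acts, any use or always use.

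Finally, 3.1.5 lists within-individual autocorrelation among the things these models allow, and permits a more complex correlation structure if needed. So within-student dependence is contemplated, but the printed model contains no term for it.

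**Conclusion.** The point holds as a gap in the definition of the primary analysis. The plan enrols students for whom the primary outcome has no value, gives no rule for them, and does not say how a ratio of counts becomes the binary response in 3.1.5. These two gaps are independent of any power figure and should be closed before analysis.

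The 456 treats all 388 retained students as evaluable. The number with a defined ratio at a given survey is 388 × f: 271, 194 or 116 at the assumed 70%, 50% and 30%. On the plan's own stated inputs, any f below 1 takes power for 0.14 below 80%. Because the stated design effect does not match the described steps, that is a statement about the printed calculation and not about the trial's true power, which the documents leave undetermined.

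**What to change.** 1. **3.1.1.** For 456 enrolled, restate the evaluable number and the detectable difference, using the past-month-active share observed at baseline with a range for 12 months. The unstated k and t and the origin of 1.3273 are a separate matter, but they must be settled before the detectable difference can be final.

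2. **3.1.5.** Model condom uses out of acts as binomial events and trials, which matches Table 2 and the 0.14. Zero-act students then contribute no trials. Add a student-level random effect so that one student's acts are not treated as independent, and a data rule for item 5.6 exceeding item 5.5.

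3. **3.1.2.** Treat the outcome as not applicable, and do not impute it, when item 5.1 is No or item 5.5 is 0. For dropouts, and where item 5.1, 5.5 or 5.6 is blank, impute past-month activity first and condom use only if active. Without this step, dropouts of unknown activity could still be assigned condom use.

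4. **Interpretation.** State that the primary comparison is conditional on past-month activity, which the intervention may change, and report the active share by period and condition. An all-student analysis of any condomless intercourse (item 5.5 greater than 5.6, no sex counted as no) is an optional supplement. It can move through abstinence alone, so it cannot replace the primary.

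5. **Time point.** Reconcile H1 in the registration receipt and progress report (12 months primary) with the receipt's outcome list (3, 9 and 12 months).

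**Cost.** SAP wording and a two-stage imputation, with no new data. Events and trials give more weight to students with more acts. The conditioning on activity is not removed, only made visible, and the restated detectable difference may be less favourable.

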**2.3.2 Study Aims.**

- **AIM 1** begins with a year of formative work to refine and tailor the components of N/E. Our community advisory board and the Fort Peck-based and MSU-based research team will design culturally appropriate adaptations for N/E's 4 levels.
- **AIM 2** tests the efficacy of N/E using a cluster-randomized stepped-wedge design (SWD), in which the 5 high schools that Fort Peck youth attend are randomized into the intervention 1 at a time. N/E's primary outcome is increased condom use during sexual intercourse. Secondary outcomes are delayed onset of sexual intercourse, number of sex partners, frequency of sexual intercourse, pregnancy history, consistent use of birth control during sexual intercourse, and whether alcohol and/or other drugs are used during sexual intercourse. Tertiary outcomes are increased parent/legal guardian-child communication about SRH topics, increased understanding of cultural values related to traditional AI beliefs regarding SRH, and increased use of SRH services. Quantitative data collection includes: student surveys at baseline, 3, 9 and 12 months; parent/legal guardian surveys at baseline, 9 and 12 months. Qualitative data collection includes SRH service provider discussion groups at baseline and thereafter once a year over the 5-year study, with logs to track coordination and implementation at baseline and 3, 6, 9 and 12 months.
- **AIM 3** will evaluate the fidelity and acceptability of N/E with focus groups, activity logs, and staff meeting notes and staff field notes.

Our **long-term goal** is to produce a toolkit, including curriculum manuals, an SRH cultural mentoring program, and specific systems-level actions suitable for replication in other tribal communities. The **public health impact** is the prevention of STIs, HIV, HCV, and teen pregnancies in AI youth resulting in reduced sexual and reproductive health disparities and improved health in AI families and communities.

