**2.3.3 Design Overview.** *NIE* is a community-based participatory research (CBPR) multi-level, multi-component sexual and reproductive health (SRH) intervention, constructed on Ecological Systems Theory. *NIE* is based on Fort Peck tribal members' desire to implement a holistic SRH intervention for AI youth. *NIE* includes: 1) A school-based SRH curriculum called *Native Stand*, designed to address **individual-level** factors that lead to sexual risk behaviors; 2) a **family-level** curriculum called *Native Voices*, tailored to increase communication between adult family members and youth about SRH topics; 3) a cultural mentoring component at the **community level** that pairs AI youth with adults and elders to discuss traditional AI beliefs and practices about SRH; and 4) a mobilizing strategy to activate a multi-sectoral network of youth-servicing organizations at the **systems level** in Fort Peck to coordinate SRH services for AI youth. The overarching aim of this study is to refine, tailor, and finalize the components of *NIE* and evaluate its efficacy. We will use a cluster-randomized stepped-wedge design (SWD), in which 5 schools that AI youth from Fort Peck attend are the clusters to be randomized into the intervention 1 at a time, with all schools eventually being randomized to the intervention. The 5 schools are located in separate communities, mitigating the potential for cross-contamination. *NIE* is a 5-year study involving 456 15- to 18-year-old AI youth.

**2.3.4 Intervention Design.** *NIE* is a 5-year CBPR ecological intervention for 456 15- to 18-year-old AI youth living on the Fort Peck Reservation. *Nen OnkUmbilEdaHiYedo* ("We Are Here Now") derives from the Assiniboine (*Nen OnkUmbt*) and Sioux (*EdaHiYedo*) names for their traditional coming-of-age ceremonies, when, at the age of 15 and over, young tribal members are believed to be ready for integrated education and training on sex, what it means to be a man or a woman, relationships, having children, and being a parent. *NIE* is guided by a 5-member CAB. The primary institutional partners responsible for the implementation of *NIE* are Fort Peck Community College (FPCC), the Fort Peck Tribes Language and Culture Program, the Fort Peck Tribal Health Department (Epi Team), and MSU.

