completed treatment. ***Following randomization of the schools to the intervention, there will be three waves of implementation: Wave 1 (1 school in 2019), Wave 2 (2 schools in 2019-2020), and Wave 3 (2 schools in 2020-2021).*** The 5 schools on the Fort Peck Reservation will be the clusters that are randomized to *NIE*. *NIE* will take approximately 40 weeks, or 3 quarters, to implement. The first observation period (Q4 of Year 2) provides baseline measurements for all respondents drawn from every cluster. The cluster is then surveyed at 3, 9, and 12 months for the students in the cluster once they have begun participation in the intervention, and at 9 and 12 months for the parents/legal guardians in the cluster once they have begun participation in the intervention. Following completion of the intervention across all clusters, we will conduct the quantitative analysis. The SWD allows us to control for the effect of time and ensure that the full AI population of schools at Fort Peck receives *NIE*. The systems-level component of *NIE* will be implemented reservation-wide rather than school-wide during Years 2 to 4 of *NIE* as the SWD is rolled out. The systems level component will be measured and analyzed qualitatively.

**2.3.6 Trial Timeline.** The timeline for *NIE* is: Year 1-Refine, tailor, and finalize the components of *NIE* with the CAB by reviewing our current quantitative and qualitative data from Fort Peck and by talking with elders

[figure not shown]

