**Figure 4. Trial design and timeline for implementing N/E relative to grant and sites/schools.**

*Nenunkumbi/Edahiyedo ("We Are Here Now"): A Multi-level, Multi-component Sexual and Reproductive Health Intervention for American Indian Youth*

and community stakeholders. We will have monthly team meetings and quarterly CAB meetings. When necessary, we will meet with CAB members individually. We will also recruit, hire, and train staff in *Native Stand* and *Native Voices*; identify the cultural mentors; purchase all necessary materials and supplies; finalize research protocols and IRB approvals. Years 2, 3, and 4- Collect baseline data; Implement *NIE*; conduct quantitative and qualitative data collection; conduct ongoing fidelity and acceptability data collection; and continue monthly team meetings and quarterly CAB meetings. Year 5-Finish data collection; conduct data analysis; work with CAB on interpretation of data analysis; develop sustainability plan; develop intervention toolkit; and disseminate results to scientific, professional, and Fort Peck communities. See Appendices for *NIE* timeline.

**2.3.7 Sample Size and Population.** *NIE*'s sample size is 456 AI male and female youth ages 15 to 18 years old. The population of AI youth 15 to 18-year-old attending the five schools participating in the study is approximately 617.

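### The design effect of 1.3273 behind N = 456 is out of reach of the printed formula for three waves or for five single-school steps, so the stated 80% power does not come from the trial described

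*Combined protocol and SAP*

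**What the plan says.** Section 3.1.1 sets the total at an uncorrected number of students, Nu, times a stepped-wedge design effect. Nu is the number needed to "detect the treatment effect with a power of 80% and a significance level of 0.05". The design effect is printed as

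DE = [1 + ρ(ktn + bn − 1)] / [1 + ρ(½ktn + bn − 1)] × 3(1 − ρ) / [2t(k − 1/k)],

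where k is the number of steps, t the measurements after each step, b the baseline measurements, and n "is the expected number of students per cluster". The intra-class correlation ρ is put at 0.016. The section then gives Nu = 292, DE = 1.3273 and 15% attrition, and states that "a sample size of 456 will allow the detection of a 0.14 increase in the proportion of condom use". It gives no values for k, t, b or n.

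The step count has to be taken from the design sections, which give two versions:

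- Section 2.3.5 (Trial Design) has three waves: "Wave 1 (1 school in 2019), Wave 2 (2 schools in 2019-2020), and Wave 3 (2 schools in 2020-2021". The three arms in the registration record in the appendices match this.
- Section 2.3.2 (Study Aims) says "the 5 high schools that Fort Peck youth attend are randomized into the intervention 1 at a time", and section 2.3.3 (Design Overview) repeats the one-at-a-time entry.

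Section 2.3.5 also places a baseline before any school crosses over. After that, each school is "surveyed at 3, 9, and 12 months for the students in the cluster once they have begun participation". Section 2.3.7 says that the number of eligible youth "attending the five schools participating in the study is approximately 617".

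**The concern.** A design effect above 1 says that the stepped-wedge layout needs more students than an uncorrected calculation. In the printed formula the second factor falls quickly as the number of steps grows, and at three or more steps the result should be around or below 1. A value of 1.3273 therefore looks incompatible with either description of the trial.

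The sample size of 456, repeated throughout the protocol, rests on this figure. So does the claim of 80% power for a 0.14 increase. Readers will judge the result against that claim, a null result above all. If the design effect belongs to another design, the claim has no derivation behind it. The formula also counts measurements at each step, whereas the follow-up surveys in section 2.3.5 are tied to each school's own start. The power of the layout actually planned is then not established by any calculation in the document.

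**Working it through.** **Inputs.** From section 3.1.1: ρ = 0.016, Nu = 292, DE = 1.3273, attrition 15%, N = 456. From the design sections: k = 3 (waves) or k = 5 (one school at a time), and one common baseline, so b = 1. Assumed, because not printed: t = 1, which gives the largest design effect, and equal school sizes of 456/5 = 91.2 or, if every eligible youth enrolled, 617/5 = 123.4.

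**1. The plan's own figure.** 292 × 1.3273 = 387.57, and 387.57 / 0.85 = 455.97, which rounds to 456. The last step reproduces, so the fault must lie in the design effect.

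**2. Upper bound.** Write A = 1 + ρ(bn − 1) and B = ρktn. The first factor is (A + B)/(A + B/2). Since A > 0, it is always below 2. Hence

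DE < 3(1 − ρ) / [t(k − 1/k)],

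which is largest at t = 1:

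| k | 3 × 0.984 / (k − 1/k) | Ceiling |
|---|---|---|
| 3 | 2.952 / 2.6667 | 1.107 |
| 4 | 2.952 / 3.75 | 0.787 |
| 5 | 2.952 / 4.8 | 0.615 |

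No n, b or t gives 1.3273 with three or more steps.

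**3. Values at plausible inputs** (ρ = 0.016, b = 1, t = 1).

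- k = 3, n = 91.2: 6.8208/4.6320 × 0.5535 = 0.815.
- k = 5, n = 91.2: 9.7392/6.0912 × 0.3075 = 0.492.
- n = 123.4: 0.830 (k = 3) and 0.500 (k = 5).

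At n = 91.2 the ratios are 1.3273/0.815 = 1.6 and 1.3273/0.492 = 2.7. If t = 3 is used instead, for the three follow-up surveys, the formula gives 0.319 and 0.186, further still from 1.3273.

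**4. The second value of ρ.** The same paragraph later gives ρ as 0.05, probably meaning alpha. Taken as the correlation, it lowers the ceilings to 1.069 (k = 3) and 0.594 (k = 5).

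**5. What does give 1.3273.** A search over k = 2–10, t = 1–5, b = 0–5 and n = 1–1000 at ρ = 0.016 has one match to four decimals: k = 2, t = 1, b = 1, n = 71, with DE = 1.32731. At ρ = 0.05 there is none. If 0.016 is a rounded value (0.0155 to 0.0165), the nearest match for k = 2, t = 1, b = 1 moves between n = 73 and n = 69; k = 3 and k = 5 remain out of reach. This is an inference about the inputs. The text describes neither two steps nor 71 students per school (71 × 5 = 355).

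**6. Nu = 292.** Neither the baseline proportion (or SD) nor the sidedness is printed. For a two-sided 5% test of two proportions at 80% power, a 0.14 increase needs a total of about 290 if the baseline is near 0.17 or 0.69, and about 370 to 400 if it is between 0.30 and 0.43. Nu cannot be checked as it stands.

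**The case against.** The strongest reply is that the error runs in the safe direction. With the formula's own values at n = 91.2 and t = 1, the required total would be 292 × 0.815/0.85 = 280 for three steps, or 292 × 0.492/0.85 = 169 for five, both well under 456. On that view this is a traceability fault with no harm to the trial.

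The direction is right: the formula does not show that 456 is too small. But the smaller design effects cannot be credited to this trial either. In section 2.3.5 a school has a common baseline and then surveys at 3, 9 and 12 months after its own start. No survey of schools still waiting is described between baseline and their start. The formula's measurements after each step do not describe that schedule.

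Two smaller objections are fair. The ratios of 1.6 and 2.7 depend on t = 1, b = 1 and equal schools, though t = 1 is the choice kindest to the plan and the ceilings need none of these assumptions. The two-step match is reverse-engineered, and the trial-design figure and appendix timeline were not visible in the text reviewed; the conclusion rests on the bound and on the written step counts, not on that match.

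**Conclusion.** The point holds. The stated design effect of 1.3273 exceeds the printed formula's maximum of 1.107 for three steps and 0.615 for five. That result needs only the formula, the stated correlation of 0.016 and the step counts in the design sections. At about 91 students per school, one baseline and one measurement per step, the stated value is 1.6 or 2.7 times what the formula returns. The sample size of 456 follows from 1.3273, but 1.3273 does not follow from the trial described.

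The 80% power for a 0.14 increase is therefore unsupported. Whether true power is higher or lower is not known: it depends on the real survey layout, the school sizes and the unstated baseline. This should be corrected before the power statement is relied on.

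**What to change.** Keep N = 456 and restate what it can detect.

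- Compute power, or the detectable difference, directly from the layout of section 2.3.5: one, two and two schools, the common baseline, the surveys at 3, 9 and 12 months after each school's start, and the expected size of each school.
- Align the one-at-a-time wording in sections 2.3.2 and 2.3.3 with the three waves, so that one step count holds throughout.
- Print the number of steps, the baseline and post-step measurements, students per school, the sidedness of the test, and the baseline proportion or SD behind Nu = 292.
- Correct the second value of ρ (0.05) to alpha, if that is what was meant.

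The cost is a recalculation and revised SAP wording. Enrolment does not change.
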